6.2 DETAILS OF TRIAL PROCEDURES AT SELECTED VISITS

Study procedures to be performed at each visit are listed in the [Flow Chart](#) and the respective protocol sections. Refer to Section 5 for explanations of procedures. Additional details on procedures at selected visits are provided below.

6.2.1 Screening and run-in period(s)

Screening Period

Once the patient has provided informed consent (before any trial-specific procedures or assessments are performed), meets the inclusion criteria and does not meet the exclusion criteria (see Section 3.3), the following will be performed/collected:

- Demographic information (including gender, date of birth, ethnicity, and race), and medical and surgical history (including psoriasis history and history of opportunistic infection)
- Infection screen (TB, HBsAg, anti-hepatitis B core antibodies [anti-HBc], anti-HCV, and HIV test, per the investigator's discretion)
- Chest X-ray, unless taken within the previous 12 weeks
- TB test
- Serum pregnancy test for women of child-bearing potential
- Physical examination, including height (cm) and weight (kg)
- Vital signs (blood pressure, pulse rate, and body temperature)
- Laboratory testing (serum chemistry, hematology, and urinalysis)
- 12-lead ECG
- Previous and concomitant therapy
- Assessment of AEs
- Efficacy assessments: PASI, sPGA, DLQI,

Once patients have completed screening, have met all the inclusion criteria and none of the exclusion criteria, randomization can occur through a registration call through a standard randomization visit call, using the IRT system. The Day 1 randomization or registration call will depend on the trial site procedure. Patients will be randomized to each treatment in a 1:1 ratio (BI 695501: US-licensed Humira) according to the stratification factors. The registration call can be made within 10 days prior to the planned first administration of trial medication. Eligible patients will then be confirmed to the randomization scheme on Day 1 (or when the drug is at site), according to their randomization. Eligible patients will be randomized in blocks to double-blind treatment at Day 1 according to the randomization. Patients will be randomly assigned in a blinded fashion to BI 695501 or US-licensed Humira.

6.2.2 Treatment period

Baseline, Visit 2 (Day 1)

For the duration of the trial, BI 695501 / US-licensed Humira will be administered by a suitably qualified, designated trial personnel, either at the site or at the patient's home.

Eligible patients will be randomized and will receive their first administration of trial medication on Day 1.

The following will also be performed/collected:

- Urine pregnancy test for women of child-bearing potential
- Physical examination (see Section 5.3.1)
- Vital signs
- Laboratory testing (serum chemistry, hematology and urinalysis)
- Previous and concomitant therapy (see Section 4.2)
- Assessment of AEs (see Section 5.3.6)
- Previous and concomitant therapy
- Efficacy assessments: PASI, sPGA, DLQI, (see Section 5.2)
-

- Contact IRT
- The first injection of trial medication

Visit 3

The following will be performed/collected:

- Assessment of AEs and concomitant therapy
- Contact IRT, training and administer trial medication

Visits 4 to 9

On study days with self-administration of BI 695501 or Humira, patients must complete a patient diary. This occurs on Weeks 3, 5, 7, 9, 11, 13, 15, 17, 19, 21 and 23. Trial site personnel will instruct the patient on how to complete the patient diary. The purpose of the diary is to record events occurring between site visits. Patients will be instructed to accurately record the dates and times of trial medication dosing; problems encountered with dosing; the occurrence of any AEs; the use of concomitant therapies; and the prefilled syringe storage conditions on the provided diary cards between the site visits. The patient will be instructed to contact the site if they are experiencing any AEs between designated site visits.

The following will be performed/collected:

- Urine pregnancy test for women of child-bearing potential (Visits 5, 7, 9)

- Physical examination (Visits 5, 7, 9)
- Vital signs (blood pressure, pulse rate, and body temperature; see Section 5.3.2) (Visits 5, 7, 9)
- Laboratory testing (serum chemistry, hematology and urinalysis; see Section 5.3.3) (Visits 5, 7, 9)
- 12-lead ECG (Visits 5, 7, 9) (
- Assessment of AEs and concomitant therapy
- Review of the patient diary card entries
- Efficacy assessments: PASI, sPGA, DLQI; (see Section 5.2)
-
- Contact IRT and administer trial medication (see Section 4.1.4)

The patient will return all used and unused trial medication at each visit after Week 4 and will bring his / her patient diary for review. Prefilled syringes will be collected by the trial site personnel and destroyed in accordance with local requirements, as instructed in the ISF.

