Abbreviations: ; AE=adverse event; anti-HBc=anti-hepatitis B core antibodies; anti-HCV=anti-hepatitis C antibodies; DLQI=Dermatology Life Quality Index; EoT=End of Treatment; IRT=Interactive Response Technology; HBsAg=hepatitis B surface antigen; HIV=human immunodeficiency virus; IGRA=interferon gamma-releasing assay; ; PASI=Psoriasis Area and Severity Index; PPD=purified protein derivative; SFU=Safety Follow-up; sPGA=Static Physician's Global Assessment of psoriasis; TB=tuberculosis.

1. Patients will have to visit the site for efficacy assessments and to provide samples for / safety. For other visits (Weeks 3, 5, 7, 9, 11, 13, 15, 17, 19, 21 and 23), patients are allowed to self-administer the drug at home (after training).
2. Patients who discontinue the trial early (also those not achieved PACI 50 at week 16) will, at discontinuation, have an End of Treatment (EoT) Visit equivalent to the Week 24 assessments (except trial medication administration). Every effort should be made for all patients to return for a Safety Follow-up (SFU) Visit 10 weeks after last drug administration.
3. All efficacy (e.g., PASI, and sPGA) and safety assessments will be performed by blinded personnel.
4. A chest X-ray is to be taken at Screening. Alternatively, results from a chest X-ray taken within 12 weeks of Screening can be used.
5. Patients must have a negative tuberculosis (TB) screening assessment, including a purified protein derivative (PPD) skin test or interferon gamma-releasing assay (IGRA) (e.g., QuantiFERON[®] TB Gold or T-SPOT[®].TB). In addition, a TB test can be performed at any time during the trial if the investigator considers it clinically necessary.
6. Vital signs include measurement of body temperature, blood pressure, and pulse rate (all in the sitting position after a 5-minute rest).
7. Adverse events (AEs) will be collected from the time of informed consent. Adverse events continuing at the SFU Visit must be followed to resolution or followed up as agreed by the investigator and medical monitor. For patients who complete the trial or who discontinue the trial early, new AEs will be captured for up to 10 weeks after last drug administration (SFU Visit).
- 8.
9. Trial medication should be administered at Day 1, with the second injection 7 days later and subsequent injections every 2 weeks thereafter (\pm 2 days up to Week 14 and \pm 3 days from Week 16 onward).

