4.1.4 Drug assignment and administration of doses for each patient

Each patient will receive 80 mg of BI 695501 or US-licensed Humira at the Baseline Visit (Day 1, Week 0) followed by 40 mg of BI 695501 or US-licensed Humira 1 week later, and then 40 mg of BI 695501 or US-licensed Humira every other week until Week 16 (primary endpoint).

After Week 16 (Day 112), patients achieving at least a PASI 50 response will continue receiving their randomized treatment (40 mg BI 695501 or Humira every other week) until Week 24 in a blinded fashion.

Patients not achieving at least PASI 50 at Week 16 will not be further treated with the study drugs, but only followed up for safety.

The prefilled syringe must be removed from refrigeration 30 minutes before administration to permit the medication to warm. Injecting cold medication can cause discomfort. Once taken out of the refrigerator, the trial medication should be administered within 1 hour. A syringe must not be used if it is frozen or if it has been left in direct sunlight.

The patient will administer the injection in an area of the skin where post-administration assessments of any reaction would not be compromised by the presence of impairment to skin integrity. The location for the trial medication injection will be the lower abdomen (excluding a 2-inch [5-cm] area around the navel) and upper thigh. A different injection site should be selected for each injection (at least 1 inch [2.5 cm] away from the previous site).

For the duration of the trial, trial medication will be administered either at the trial site by dedicated trial personnel, or at home by the patients themselves. At all designated site visits (Weeks 0 and 1), the patient must administer BI 695501 while at the trial site. Between designated site visits (Weeks 3, 5, 7, 9, 11, 13, 15, 17, 19, 21, and 23), the patient may choose to come to the site to self-inject the trial medication with the support of suitably qualified, designated trial site personnel or the patient may self-inject the trial medication at home. Patients will be instructed to accurately record the dates and times of dosing, problems encountered with dosing, the occurrence of any AEs, the use of concomitant therapies, and the prefilled syringe storage conditions on the provided diary cards between the trial site visits.

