For self-administration, handling and administration of trial medication will be described in detail in the handling instructions. Cool bags and handling instructions will be provided to the patient (refer to the ISF).

In case of implementation of the third-party blinded procedure, for the duration of the trial, BI 695501 / US-sourced Humira will be administered by a dedicated trial personnel (designated unblinded person will administer the drug to patients but will not be involved in any assessment of safety or efficacy), either at the site or at the patient's home. These trial personnel will be allowed to perform drug administrations and home visits only after suitable training has been received and they are considered to be qualified to perform the subcutaneous injections and the home visits.

After the first injection (Visit 2), the patient will remain at the clinical site for at least 1 hour for observation of any AEs.

Dose modification is not permitted during this trial. If a patient misses a dose of trial medication then the dose should be administered as soon as possible.

The 2-week regimen for trial medication administration should resume from the time the last dose is administered. The last injection is planned to occur at Week 23 for all eligible patients. The treatment period will not be extended past this time point.

In the event of an anaphylactic or other serious hypersensitivity reaction, the administration of trial medication will be discontinued immediately, the patient will be discontinued from the trial and appropriate therapy will be initiated.

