4.3 TREATMENT COMPLIANCE

Compliance on study visit days (Weeks 0 and 1) will be assured by the observation of trial medication administration by dedicated trial personnel considered qualified to perform or observe the subcutaneous injections.

Between designated site visits (Weeks 3, 5, 7, 9, 11, 13, 15, 17, 19, 21 and 23), the patient may self-inject the trial medication at home. Patients will be instructed to notify the site if they miss a dose or receive a partial dose so the Investigator can determine any necessary follow-up. For all trial medication injections, patients will be asked to complete a patient diary documenting the date and time of the injections and problems encountered with dosing (missed or incomplete injections should be recorded as well).

All used and unused syringes must be returned to the site at each visit.

Patients showing poor compliance as assessed by missing their allocated days for trial medication administration must be counseled on the importance of good compliance to the trial dosing regimen.

Subjects who are non-compliant (for instance, who do not appear for scheduled visits or violate trial restrictions) may be removed from the trial by the investigator after consultation with the sponsor or sponsor's representative, and the eCRF will be completed accordingly.

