6.2.3 Follow-up Period and Trial Completion

Patients who discontinue the trial prematurely at any time after Day 1 including patients with discontinued treatment at week 16 due to lack of efficacy (but do not withdraw their consent) will, at discontinuation, have an End of Treatment (EoT) Visit equivalent to the Week 24 assessments (except trial medication administration). Patients who discontinue the trial will also be required to have all of the evaluations planned for Visit 10 (Week 34) 10 weeks after their last administered dose of trial medication. These patients should be registered as prematurely discontinued in IRT.

The following will be performed/collected:

- Urine pregnancy test for women of child-bearing potential
- Physical examination, including weight (kg) (see Section 5.3.1)
- Vital signs
- Laboratory testing (serum chemistry, hematology, and urinalysis)
- Previous and concomitant therapy (see Section 4.2)
- Assessment of AEs and concomitant therapy
- Review patient diary
- TB test

Unscheduled visit assessments

Patients may attend the trial site for unscheduled visits at any time for additional safety monitoring at the discretion of the investigator.

All abnormal values that are judged clinically relevant by the investigator will be monitored using the appropriate tests until a return to a medically acceptable level is achieved. Adverse

events persisting after trial completion must be monitored until they have normalized or have been sufficiently characterized.

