14.1. DERIVATIONS

Compliance with trial medication will be based on the eCRF page “Trial Medication Injection”. An administered injection is considered when the question “Was full dose given” is answered “Yes”.

Compliance will be based on the comparison of actual administered injections and the planned usage. Compliance will include visits until treatment discontinuation.

- “Per visit” compliance will be calculated as follows and will correspond to the observed compliance between visit N and N-1:

Compliance (%) = (Number of administered injections at visit X) * 100 / Planned number of injections at visit X

Planned usage is detailed below.

- “Overall” compliance will be calculated as follows:

Compliance (%) = (Number of administered injections) * 100 / Planned number of injections

Where

Planned usage

Visit N	1	2	3	4	5	6	7	8	9
---------	---	---	---	---	---	---	---	---	---

Document: \\eedc-nas01a:\Boehringer_Ingelheim\BI_695501\XXA39605\Biostatistics\Documentation\SAP\15-v2.0\BI 1297.12 SAP v2.0 31JAN2018.docx

Author: Version Number: 2.0
Version Date: 31JAN2018

Template No: CS_TP_BS016 Revision 4
Effective Date: 01Apr2016

Reference: CS_WI_BS005

Number of injections between visit N and N-1	-	2	1	1	2	2	2	2	2
Planned cumulative number of injections	0	2	3	4	6	8	10	12	14

- “Week 16” compliance will be calculated considering the injections until Week 16 (visit 7) (included).

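### The protocol contradicts itself on dosing days: the Visits 4 to 9 list in 6.2.2, the Week 24 wording and Table 4.1.1: 1 do not match the Weeks 0, 1, 3, 5 … 23 schedule used elsewhere

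*Protocol*

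**What the plan says.** **Passages pointing to doses at the clinic visits or on even weeks**

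- Protocol 6.2.2, the list of procedures for Visits 4 to 9, closes with "Contact IRT and administer trial medication (see Section 4.1.4)". Five safety items in the same list (pregnancy test, examination, vital signs, laboratory, ECG) are limited to Visits 5, 7 and 9. This item has no limit.
- Flow Chart footnote 2 and Protocol 6.2.3 give early stoppers an End of Treatment "Visit equivalent to the Week 24 assessments (except trial medication administration)". That exception only makes sense if Week 24 includes a dose.
- Table 4.1.1: 1 starts the two-weekly 40 mg dose of BI 695501 at Week 2. Table 4.1.1: 2 starts it at Week 1 for Humira. Both end at Week 23.

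**Passages pointing to Weeks 0, 1, 3, 5 … 23**

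- Flow Chart footnote 9: "Trial medication should be administered at Day 1, with the second injection 7 days later and subsequent injections every 2 weeks thereafter". Footnote 1 lists the odd weeks 3 to 23 for possible home dosing.
- Protocol 4.1.4: "At all designated site visits (Weeks 0 and 1), the patient must administer BI 695501 while at the trial site", with odd weeks 3 to 23 at home or on site, and "The last injection is planned to occur at Week 23 for all eligible patients".
- Protocol 4.3: "Compliance on study visit days (Weeks 0 and 1) will be assured by the observation of trial medication administration".
- The diary sentence that opens the Visits 4 to 9 part of 6.2.2 names the same odd weeks.
- SAP 13 runs exposure from Day 1 and Day 8 to Day 162. SAP 14.1 tabulates "Number of injections between visit N and N-1", reaching 10 syringes at Visit 7 and 14 at Visit 9.

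**The concern.** Site staff work from the visit lists. The Visit 3 list in 6.2.2 uses almost the same wording for a real on-site dose at Week 1, so the text gives a coordinator some reason to read Visits 4 to 9 the same way. A clinic dose could then be given in addition to a home dose or in place of one.

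At Visit 7 the item does not itself state the PASI 50 condition for continuing treatment. At Visit 9 it falls a week after the stated last injection. The posology tables add a difference between arms, since only the test product starts at Week 2.

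Three things are at stake: patient safety; exposure before the Week 16 primary assessment, which also feeds the compliance review for the per-protocol set; and the date of the last dose, from which the 10-week follow-up and the treatment-emergent AE window are counted.

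**Working it through.** **Step 1. Which weeks are Visits 4 to 9?** SAP 14.1 identifies Visit 7 as Week 16: Week 16 compliance "will be calculated considering the injections until Week 16 (visit 7) (included)". Clinic efficacy assessments are at Weeks 4, 8, 12, 16, 20 and 24. Visits 4 to 9 are therefore those six weeks, or Days 29, 57, 85, 113, 141 and 169. The Flow Chart's trial-medication row did not survive text extraction cleanly and is not used here.

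**Step 2. Reproduce the SAP planned-usage table.** Take two syringes at Week 0 and one at each odd week from 1 to 23. Count the doses falling after the previous visit and up to the current one.

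| Visit | Week | Dose weeks in interval | Syringes | Cumulative | SAP 14.1 |
|---|---|---|---|---|---|
| 2 | 0 | 0 | 2 | 2 | 2 |
| 3 | 1 | 1 | 1 | 3 | 3 |
| 4 | 4 | 3 | 1 | 4 | 4 |
| 5 | 8 | 5, 7 | 2 | 6 | 6 |
| 6 | 12 | 9, 11 | 2 | 8 | 8 |
| 7 | 16 | 13, 15 | 2 | 10 | 10 |
| 8 | 20 | 17, 19 | 2 | 12 | 12 |
| 9 | 24 | 21, 23 | 2 | 14 | 14 |

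Every cell agrees. The SAP is built on the odd-week schedule.

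**Step 3. Overlap with Visits 4 to 9.** Dosing days (1 + 7 × week) are 1, 8, 22, 36, 50, 64, 78, 92, 106, 120, 134, 148 and 162. None equals a Visit 4 to 9 day. Each of those visits is 7 days from the nearest dosing day (29 − 22 = 7; 169 − 162 = 7), so the ±2 and ±3 day windows cannot absorb the difference.

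**Step 4. The posology tables.**

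- BI 695501, two-week steps from Week 2: Weeks 2, 4, … 22. This includes Weeks 4, 8, 12, 16 and 20, five of the six visit weeks. Week 23 cannot be reached, since (23 − 2)/2 = 10.5. Syringes: 2 + 11 = 13.
- Humira, two-week steps from Week 1: (23 − 1)/2 = 11 steps, so 12 doses. Syringes: 2 + 12 = 14, as in the SAP.

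**Step 5. Ceiling if the 6.2.2 item is applied literally on top of the odd-week schedule.**

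- Whole treatment period: 14 + 6 = 20 syringes; 20/14 = 143% of plan.
- Before the Week 16 assessment: 10 + 3 = 13; 13/10 = 130%. A Visit 7 dose is left out because Protocol 6.1 puts assessments before dosing.
- SAP Week 16 compliance, which includes Visit 7: 10 + 4 = 14; 14/10 = 140%.
- Both percentages exceed the 120% limit above which SAP 5.4 sends a patient to medical review for the per-protocol set.
- Last dose plus 70 days: 162 + 70 = Day 232 as planned; 169 + 70 = Day 239 with a Week 24 dose.

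**The case against.** The strongest reply is that a site reading the whole instruction would add nothing. The item points to 4.1.4, which lists no dose at these visits, states the PASI 50 condition, fixes the last injection at Week 23 and forbids dose modification. The same part of 6.2.2 opens by naming the odd weeks, and Section 6.2 presents itself as additional detail to the Flow Chart. IRT assigns a medication number for each administration, and contact at these visits goes with dispensing one or two syringes for home use (footnote 12). Syringes are returned and accounted for. Follow-up and AE windows are counted from the actual last dose, so a later dose would move them consistently rather than break a rule.

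Most of this stands, and it limits the likely effect. It does not remove the contradiction. The item still orders an administration under a section that has none at those visits, no order of precedence is stated, and dispensed syringes can be in the patient's hands. The Week 24 wording and Table 4.1.1: 1 are not covered by that cross-reference.

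Three stronger readings might be inferred, and the documents do not support them:

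- That none of Weeks 4 to 24 in question is a dosing day anywhere else in the plan. Table 4.1.1: 1, read literally, makes five of them dosing weeks for BI 695501, and the Week 24 exception implies the sixth.
- That six extra doses should be expected. The safeguards above make six a ceiling.
- That the odd-week schedule is therefore the correct one. More passages agree with it, and the SAP depends on it, but which schedule is intended is for the sponsor to say.

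**Conclusion.** The point holds as an internal contradiction on dosing days that needs correcting. The 6.2.2 item for Visits 4 to 9, the Week 24 exception in footnote 2 and 6.2.3, and the Week 2 start in Table 4.1.1: 1 cannot all be read together with the schedule in footnotes 1 and 9, Sections 4.1.4 and 4.3, and SAP 13 and 14.1.

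The upper bound is 6 added injections per patient (20 against 14), 3 of them before the Week 16 assessment, with SAP Week 16 compliance of 140%. This assumes that every home dose is also given, that the item is followed at all six visits, that the kits are available, and that the added injections are recorded as full doses. Following the pointer to 4.1.4 gives no added dose. The documents give no basis for a figure in between.

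The case for correction rests on the nature of the conflict, which concerns when a biologic is injected and sits partly in the list sites work from, and not on the ceiling being likely.

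**What to change.** Reconcile the following with the Flow Chart, Sections 4.1.4 and 4.3, and SAP 13 and 14.1, so that one set of dosing days appears throughout for both arms:

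- the administration item in the Visits 4 to 9 list of 6.2.2;
- the Week 24 exception in Flow Chart footnote 2 and in 6.2.3;
- the start week in Table 4.1.1: 1, which now differs from Table 4.1.1: 2.

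In the same edit, state separately what is dispensed and what is administered at each visit. Also reconcile the Baseline paragraph of 6.2.2, which has trial personnel give all doses for the whole trial, with 4.1.4, which allows home self-injection and reserves staff-only administration for third-party blinding.

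The sponsor must state which schedule is intended. If it is the one behind SAP 14.1, the cost is protocol wording and a site clarification letter, with no change to sample size, assessments or analysis. If it is another, SAP 13 and the planned-usage table in SAP 14.1 would also have to be revised.
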